#### **Adverse Drug Reaction**

An ADR is any response to a medicinal product which is noxious and unintended and which occurs at doses normally used in man for the prophylaxis, diagnosis or therapy of diseases or for the restoration, correction or modification of physiological function.

Response in this context means that a causal relationship between a medicinal product and an adverse event is at least a reasonable possibility.

Adverse reaction also includes adverse clinical consequences associated with use of the product outside the terms of the Summary of Product Characteristics or other conditions laid down for the marketing and use of the product (including prescribed doses higher than those recommended, overdoses or abuse).

### **8.2 Classifications**

#### **Seriousness**

A serious ADR or AE (SADR/SAE) is any ADR or AE which results in death, is life threatening, requires inpatient hospitalisation or prolongation of existing hospitalisation, results in persistent or significant disability or incapacity, or is a congenital anomaly or birth defect.

Life-threatening in this context refers to a reaction/event in which the subject was at risk of death at the time of the reaction/event. It does not refer to a reaction/event that hypothetically might have caused death if more severe

Medical and scientific judgement should be exercised in deciding whether other situations should be considered serious, such as important medical events that might not be immediately life-threatening or result in death or hospitalisation but might jeopardise the subject or might require intervention to prevent one of the other outcomes listed above. Examples of such events are intensive treatment in an emergency room or at home for allergic bronchospasm, blood dyscrasias or convulsions that do not result in hospitalisation, or development of dependency or abuse.

Any suspected transmission of an infectious agent via a medicinal product is considered a serious adverse reaction.

### **Severity**

Severity is a clinical observation and describes the intensity of the event.

- Mild: Transient symptoms, no interference with the subject's daily activities
- Moderate: Marked symptoms, moderate interference with the subject's daily activities
- Severe: Considerable interference with the subject's daily activities.

### **Causality**

- Related: A reasonable temporal relationship between the medicinal product administration and the event where there is no other obvious explanation for the occurrence of the event
- Not related: There is evidence for (an) alternative explanation(s) for the event (e.g. the event is explained by one or more of the following: a) the subject's medical condition (medical history, disease progress, indication), b) a concomitant medication for which the event is labelled, or c) AE occurrence prior to the introduction of the medicinal product.

### **Outcome**

- Fatal: The subject died due to the event. If the subject died due to other circumstances than the event the outcome should be stated as 'Not recovered' or 'Recovering'

- Recovered/Resolved: The subject has fully recovered from the event or the condition has returned to the level observed at baseline
- Recovering/Resolving: The event is improving but the subject is still not fully recovered
- Not Recovered/Not Resolved: The event is ongoing at the time of reporting and the subject has still not recovered
- Recovered with Sequelae/Resolved with Sequelae: As a result of the event, the subject suffered persistent and significant disability/incapacity (e.g. became blind, deaf or paralysed).
- Unknown: If Outcome is not known or not reported.

### **8.3 Reporting of Adverse Drug Reactions and Adverse Events**

The present study makes no changes to normal practice and does not include investigational medicinal products. Being a cross-sectional, non-PAS, non-interventional study, it does not require expedited reporting of suspected adverse reactions.

Nevertheless, investigators are reminded of the requirement to comply with Order SAS/3470/2009 of 16 December, which publishes guidelines on post-authorisation observational studies of medicinal products for human use, which indicates that suspected serious adverse reactions that are detected must be reported to the contact point designated by the competent body for pharmacovigilance in the autonomous community where the healthcare professional reporting the case practices, within a maximum period of 15 calendar days from said person becoming aware of the suspected adverse reaction, citing the study code.

Investigators at participating sites must send Takeda initial and follow-up reports of serious or mild adverse reactions or any other relevant safety information relating to any product marketed by Takeda (about the use of the product, with or without an associated AR, related to breastfeeding, pregnancy, overdose, misuse/abuse, medication errors, lack of efficacy and off label use ), using Takeda's adverse reactions reporting form (see appendix 5) within 24 hours of becoming aware of said reaction, and by email to **PPD** .

In the event that the CRO becomes aware of any adverse reaction or any other relevant safety information associated with a product marketed by Takeda, the CRO will be obliged to

report this to Takeda's pharmacovigilance department within 24 hours by email to PPD .

In the event that in order to evaluate an adverse reaction, the sponsor requires additional information and sends questions to the investigator at the site in question, the information provided by said investigator will be considered follow-up information on the adverse reaction and must therefore be reported to the contact point designated by the competent body for pharmacovigilance in the autonomous community where the investigator reporting the case practices, as well as to the sponsor having requested said information, with reference to the initial adverse reaction report. This report to the competent authorities and the sponsor shall be made as described in this section.

In summary, any ADRs and pregnancies observed during the study and follow-up information on these should be reported by the physician as soon as possible after having knowledge hereof directly to the authorities according to local regulations. In addition, a copy is sent to Takeda for ADRs related to a Takeda product.

No data on AEs or ADRs will be collected as part of the study database.

All safety-related data on study subjects collected in the study database or reported to Takeda according to the normal procedure for marketed drugs, e.g. serious and non-serious ADRs, must be summarised in the Non-Interventional Study Report.

## **9 Data Quality Control and Assurance**

### **9.1 Quality Control**

The application used for the collection of the data will have safety margins and internal coherence rules to avoid the entry of incorrect data or anomalous or incoherent values. A set of automatic data checks with data queries should be programmed for data cleaning. Patients will be reviewed individually, checking that all data have been collected or a reason provided where this is not the case. In the event that data are incorrect, incomplete or have not been collected in accordance with the protocol, the investigator will be asked to review and correct said data.

## 9.2 Audit from Quality Assurance Unit

The Quality Assurance (QA) unit may audit the study to ensure that study procedures comply with the protocol and standard operating procedures, and that collected data is correct and complete.

## 9.3 Inspection by IRB/IEC or Competent Authority

Representatives from IRB/IEC or Competent Authority may in rare cases wish to inspect the study on site. Upon receiving notification of such inspection, the Study Site Responsible must immediately contact Global Research and must make the records available as requested.

## 9.4 Data Management

Data Management will be carried out according to a Data Management Plan, which must be written and approved before the design of the study database is finalised. The data management provider should approve all data formats before the data collection tools are made available to the sites.

If the written informed consent of a subject is known not to be available in spite of it being required, data for this subject is not entered into or is deleted from the database.

If a subject is erroneously included in the study more than once only the data relating to the first inclusion will be kept in the database and be available for analysis. Data from later inclusions will be transferred to the first dataset when relevant, i.e. if collected within the time frame of the first follow-up period.

The current Standard Coding Instructions for coding of medical history, concomitant illness (MedDRA), concomitant medication (WHO-Drug) and adverse events/reactions (MedDRA) must be followed.

The subjects will be identified in the database only by Study ID, Site ID and subject number,

### 9.4.1 Data Collection Tools and Flow

The Study Site will receive access to electronic data capture from **CCI**. Whenever possible, complete data sets should be entered. Text field entries and any data collected should be legible and follow the requested language standard.

The Study Site Responsible must sign off the complete data set for each subject, confirming the collected data. ADR data reported according to section 7 and data on serious AE/ADR reactions collected according to section 6 should be signed off separately by a physician who may or may not be involved in the study.

### **9.5 Methods for obtaining data.**

This study entails the cross-sectional collection of data over one month at each participating site. Given the observational nature of the study, the data will be obtained in a single visit from patients' medical history and/or from the patient using the tools detailed above and in accordance with the physician's normal clinical practice.

The presence of breakthrough pain and its characterisation will be assessed using the questionnaires detailed in section H4 of the protocol in those patients who agree to participate in the study by signing the informed consent.

### **9.6 Data handling.**

In order to guarantee the confidentiality of the study data, only the following persons and entities will have access thereto: the investigator and his/her staff, the sponsor or a person designated by the sponsor, the IEC, the relevant healthcare authorities and the persons responsible for analysing the data.

The content of the CRFs, as well as the documents generated during the study, will be protected against non-permitted use by persons not involved in the investigation and will therefore be considered strictly confidential and will not be revealed to third parties.

The investigator must make sure to maintain patients' anonymity and protect their identity from unauthorised parties. Patients will not be identified by name on the CRFs, but by an identification code. The investigator must keep a record of patient recruitment, including the codes assigned for participation in the study.

The investigator will organise the safeguarding of the study documentation until the end of the study. He/she must also comply with the local standards/recommendations regarding the safeguarding of patients' records.

The processing of data of a personal nature required for this study is subject to Organic Law 15/1999 of 13 December on Personal Data Protection.

## **10 Statistical Methods and Determination of Sample Size**

This section describes the statistical analyses as foreseen at the time of planning the study. Any known deviations from the planned analyses, the reason for such deviations and all alternative / additional statistical analyses that may be performed as well as the final statistical analysis must be described in a revised Statistical Analysis Plan (SAP) before completion of data collection.

### **10.1 Statistical Analysis Plan**

This study is observational and epidemiological methods will be employed for data analyses.

Descriptive analysis will be performed of all collected data except data collected only for the purpose of data cleaning.

For a period of one month, each investigator must identify patients with cancer pain being treated with opioids who attend consultations in in Medical Oncology, Hematology, Radiotherapeutic Oncology Departments, Pain Units and Palliative Care Units, using the Davies diagnostic algorithm [3] to confirm the presence of breakthrough pain. All patients who attend pain consultations with cancer pain during this period will be used to determine the incidence/prevalence of breakthrough pain.

All patients who meet the selection criteria and have given their informed consent will be included in the breakthrough pain characterisation and quality of life study.

Before beginning the statistical analysis of the data, a Statistical Analysis Plan will be prepared, detailing all the analyses to be performed.

The incidence/prevalence of breakthrough pain and corresponding 95% confidence interval will be calculated as the percentage of subjects presenting breakthrough pain among patients with cancer pain controlled with opioids, collected by each investigator on the corresponding page of the CRF over one month. This incidence/prevalence will also be

calculated by age group and sex. It will also be made an analysis by specialty to see the difference between the various participating specialties.

The incidence/prevalence of breakthrough pain and corresponding 95% confidence interval will also be calculated relative to the number of cancer patients, collected by each investigator on the corresponding page of the CRF over one month.

Given the descriptive nature of the study, the statistical methodology used will be based primarily on an exploratory analysis of the data through the calculation of descriptive parameters.

Initially, a descriptive analysis of the study variables will be carried out and the values of the continuous variables will be summarised in a table showing the mean, median, standard deviation and maximum-minimum range for each. The categorical variables will be presented as absolute frequencies and percentages.

The assessment of breakthrough pain intensity will be performed using the scores obtained on the numerical rating scale. A description of the scores will be given using the mean, median, standard deviation, maximum and minimum.

Each of the items on the BPI questionnaire and Alberta scale will be described, using the mean, median, standard deviation and range to describe the continuous variables and frequency distributions and percentages to describe the categorical variables.

The SF-12 quality of life scale consists of 12 items, from which total scores for the physical and psychological components are obtained. The correction methods indicated in the scale's validation manual will be used for the total score for each sub-scale, and the mean, median, standard deviation and range will be presented.

Breakthrough pain in patients with cancer pain will be characterised based on aetiology and pathogenesis, as well as other clinical characteristics (type of breakthrough pain, number of episodes per day, duration and intensity, and pain management). This information will be collected with the tools used for the clinical assessment of breakthrough pain.

Given the special characteristics of the elderly population and patients with multiple myeloma, a sub-analysis of pain characterisation will be performed in patients over 70 years of age and in those with multiple myeloma.

The percentage of patients who present the various profiles/types of breakthrough cancer pain (characterisation/classification) and the causes for the same will be determined.

The percentage of patients with the various profiles/types of breakthrough cancer pain will be given based on demographic characteristics and other clinically significant variables relating to the cancer diagnosis (tumour type, stage, etc.), pain intensity, comorbidities, etc. The quality of life of patients with cancer breakthrough pain will be analysed based on its possible relationship with demographic characteristics and other clinically significant variables related to the cancer or to the breakthrough pain such as aetiology, frequency of episodes, pain intensity, time until peak of pain, crisis duration, cause, etc.

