## 2 Introduction

Oncology consultations are generally short in duration (20-30 minutes). The primary consideration for most oncologists during this time is treatment of the tumour: the choice of treatment to be administered to the patient (chemotherapy, radiotherapy, etc.), the administration of recommended treatment, and the monitoring and control of the efficacy and safety of these treatments, principally in relation to tumour response and survival [4].

Symptoms, such as pain, are often given less attention during diagnosis and treatment. Pain is one of the most common symptoms of cancer [5-7]. However, published estimates of the prevalence of pain in outpatients are inconsistent and vary between 18% and 62%, probably due to differences between the various selection criteria, the use of dissimilar assessment tools and/or different tumour stages [5-7].

Breakthrough pain is understood as the temporary exacerbation of pain occurring either spontaneously or in relation to a specific, predictable or unpredictable trigger in spite of relatively stable and adequately controlled baseline pain.

Breakthrough cancer pain is a common and distressing subtype of pain that affects a percentage of patients with cancer that varies between 40% and 90% according to different publications [1, 2]. The type of breakthrough pain seen in cancer is described as “a temporary increase in pain with an intensity above that considered moderate, overlying baseline pain of moderate or low intensity” in cancer patients treated with opioids [8].

Breakthrough cancer pain is a high intensity, short duration pain that manifests in several daily episodes and does not respond to normal treatment. The clinical approach to breakthrough cancer pain is changeable. The data show that daily exacerbations of pain need to be monitored closely, differentiating where possible between fluctuations in baseline pain and the end-of-dose effect [9].

The causes of cancer breakthrough pain are the same as those of cancer pain, and they can be related to the neoplasm, with diagnostic tests, treatment or other concomitant problems concurrent with cancer [10]. In terms of physiology, breakthrough pain may be nociceptive, neuropathic or mixed [10].

Even today, clinical focus in breakthrough pain varies considerably between clinics, from complete denial of its existence to overestimation [9].

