**4.1 Study Sites**

[figure not shown]
The study is planned to be conducted in 66 Sites in Spain (33 Hospitals), Medical Oncology, Hematology, Radiotherapeutic Oncology Departments, Pain Units and Palliative Care Units. Global Research will keep a record of the individuals responsible for each participating Study Site, the Site Responsibles.

[figure not shown]

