## **10.3 Determination of Sample Size**

We estimate that more than 10 patients per day attend consultations for cancer in Medical Oncology, Radiotherapeutic Oncology, Hematology and Palliative Care Departments and around 5 patients in Pain Units, and each site shall have a recruitment period of 1 month. Cancer breakthrough pain is a common and incapacitating subtype of pain that affects a percentage of patients with cancer that varies between 40% and 90% according to different publications [1, 2]. Conservatively, we hope to detect the prevalence in 50% of patients, and we estimate that at each site a total of approximately 200 patients, or around 13,200 across the 66 planned sites, will be interviewed on the prevalence of breakthrough pain. This sample will enable us to detect the prevalence of breakthrough pain with a 95% confidence interval and precision of  $\pm 1\%$ .

For the assessment of the secondary objective, i.e., characterising the breakthrough pain based on aetiology, underlying pathology and other clinical characteristics (type of breakthrough pain, number of episodes per day, duration and intensity, comorbidities and baseline pain management), if we consider the detection of common characteristics in at

least 10% of patients in our population to be representative, it will be necessary to recruit 529 patients in order to detect said characteristics with a 95% confidence interval and precision of  $\pm 2.5\%$ .

All patients recruited for characterisation of breakthrough cancer pain will be newly diagnosed and previously untreated for breakthrough cancer pain, although patients may be recruited who have been treated for breakthrough cancer pain in the past but are not currently being treated (at least 1 month wash-out) to avoid possible distortions in the classification of pain that may result from treatment.

Patients eligible to participate in the study must meet all the selection criteria, have a confirmed diagnosis of breakthrough cancer pain based on the Davies algorithm and must have given their informed consent in writing.

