### 5.1. Primary objective analysis

In the prevalence study the following variables will be collected:

- Patient with cancer pain: yes/no
- Breakthrough cancer pain: yes/no
- Diagnostic of BCP: Previously diagnosed; Diagnosed during the visit (according Davies algorithm)
- Date of visit.
- Age.
- Gender.
- Karnofsky PS (0 to 100).
- Type of tumour: head and neck, colorectal, esophagus, stomach, liver, leukemia, lymphoma, breast, multiple myeloma, bone and muscular, ovarian, pancreas, prostate, lung, kidney, central nervous system, testicle, uterus, bladder and other).
- Stage (I-IV).

The prevalence of breakthrough cancer pain and corresponding 95% confidence interval (95%CI) will be calculated as the percentage of subjects presenting breakthrough pain among patients with cancer pain controlled with opioids, collected by all investigators over one month.

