#### Formula:

Prevalence of breakthrough cancer pain (%) = [Number of patients with breakthrough cancer pain / total number of patients registered with cancer pain] x 100.

The estimated annual prevalence will be calculated relative to the population of cancer patients with or without pain seen over one month.

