## 5.2. Secondary objective analysis

To describe the population the following variables will be analyzed:

- o Patient with cancer pain: yes/no
- o Breakthrough cancer pain: yes/no
- o Diagnostic of BCP: Previously diagnosed; Diagnosed during the visit (according Davies algorithm)
- o Date of visit.
- o Age.
- o Gender.
- o Karnofsky PS (0 to 100).
- o Type of tumour: head and neck, colorectal, esophagus, stomach, liver, leukemia, lymphoma, breast, multiple myeloma, bone and muscular, ovarian, pancreas, prostate, lung, kidney, central nervous system, testicle, uterus, bladder and other).
- o Stage (I-IV).

In the prevalence study we will calculate the following results:

- The prevalence of breakthrough cancer pain (primary objective) according to gender (separately for men and women) and corresponding 95%CI.
- The prevalence of breakthrough cancer pain (primary objective) according to age (separately for the following categories: < 70years; ≥ 70years) and corresponding 95%CI.
- The prevalence of breakthrough cancer pain (primary objective) according to specialty (separately for the following categories: Medical Oncology, Hematology, Radiotherapeutic Oncology Departments, Pain Units and Palliative Care Units) and corresponding 95%CI.
- The prevalence of breakthrough cancer pain (primary objective) according to Karnofsky PS (separately for all categories of PS) and corresponding 95%CI.
- The prevalence of breakthrough cancer pain (primary objective) according to type of tumour (separately for all categories of type of tumour) and corresponding 95%CI.
- The prevalence of breakthrough cancer pain (primary objective) according to Stage (separately for I, II, III and IV) and corresponding 95%CI.
- The prevalence of new cases of breakthrough cancer pain and corresponding 95%CI.

Formula:

Prevalence of new cases of breakthrough cancer pain (%) = [Number of patients with breakthrough cancer pain that were diagnosed during the visit / total number of patients registered with cancer pain] x 100.

- The prevalence of breakthrough cancer pain over the total of patients with cancer and corresponding 95%CI.

Formula:

Prevalence of breakthrough cancer pain (%) = [Number of patients with breakthrough cancer pain / total number of patients registered with cancer] x 100.

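### Specialty is an attribute of the department, but the plan gives pooled patient-level percentages and CIs by specialty with no site term, so chance variation between departments could be read as a specialty difference

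*Protocol*

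**What the plan says.** Protocol 10.1 announces the breakdown: "It will also be made an analysis by specialty to see the difference between the various participating specialties". SAP 5.2 implements it as "The prevalence of breakthrough cancer pain (primary objective) according to specialty", listing the five specialties separately, each with a 95% CI. The same list gives gender, age, Karnofsky status, tumour type and stage.

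The estimator in the SAP's primary analysis is a ratio of patient counts, "Number of patients with breakthrough cancer pain / total number of patients registered with cancer pain] x 100", over data "collected by all investigators over one month". The CAT3 table shell has columns for N, % and the two confidence limits. No formula for the interval is given.

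Protocol 4.1 plans 66 sites, which are departments or units, in 33 hospitals. Protocol 10.3 sizes the prevalence part as follows: "we estimate that at each site a total of approximately 200 patients, or around 13,200 across the 66 planned sites", with a claimed precision of ±1%. The Introduction says that "clinical focus in breakthrough pain varies considerably between clinics, from complete denial of its existence to overestimation".

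No readable section of either document mentions clustering, an intracluster correlation, a design effect, a robust variance, a site effect or a department-level summary.

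**The concern.** Every patient seen in a department has that department's specialty, and the department's investigator confirms whether breakthrough pain is present. A contrast between specialties is therefore a contrast between groups of departments. Its replication is the number of departments, which is a dozen or so per specialty and not hundreds of patients. An interval computed from the pooled count contains only patient-level sampling error. If departments of the same specialty differ among themselves, that interval is too narrow for any comparison meant to describe specialties.

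At stake is the reading of the specialty table. Narrow intervals that do not overlap invite the conclusion that prevalence differs by specialty, when the data may show only that a few departments differ from a few others. The Introduction attributes disparate published prevalences partly to single-specialty studies, so readers are likely to look at this table.

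**Working it through.** **1. The plan's own precision figure.** 66 × 200 = 13,200 patients. At 50% prevalence the half-width is 1.96 × √(0.25/13,200) = 0.85 points, which rounds to the stated ±1%. The claim is met on the assumption that patients are independent. This is the main evidence for what kind of CI is intended.

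**2. Departments per specialty.** The split is not given. Protocol section 7 gives quotas of 120 patients per specialty (60 in Hematology), at 10 per investigator (5 in Pain Units). Assuming one investigator per site:
- Medical Oncology, Radiotherapeutic Oncology, Palliative Care: 120/10 = 12 each
- Hematology: 60/10 = 6
- Pain Units: 120/5 = 24

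The total is 36 + 6 + 24 = 66, which matches the planned number of sites exactly.

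**3. Cancer-pain patients per site (m).** The Introduction puts pain in outpatients at 18 to 62%. Of 200 attenders that is 36 to 124, with midpoint 80. Pain Units see about half the daily volume (Protocol 10.3), so m/2 is used there.

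**4. ICC.** The documents give none. The range 0.01, 0.05, 0.10 is an assumption.

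**5. False-positive rate of a patient-level comparison when there is no true difference.** Prevalence is 50%. With D = 1 + (m − 1) × ICC for each specialty and n its number of patients, the true variance of the difference exceeds the binomial variance by

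R = (D₁/n₁ + D₂/n₂) / (1/n₁ + 1/n₂),

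and the error rate of a nominal 5% test is 2 × [1 − Φ(1.96/√R)].

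Example: Medical Oncology against Hematology, m = 80, ICC 0.05. Both D are 1 + 79 × 0.05 = 4.95, so R = 4.95, 1.96/√4.95 = 0.88, and the rate is 38%. Against Pain Units (m = 40, D = 2.95; n = 960 on both sides), R = (4.95 + 2.95)/2 = 3.95 and the rate is 32%.

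Medical Oncology compared with another specialty:

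| ICC | Other specialty | m = 36 | m = 80 | m = 124 |
|---|---|---|---|---|
| 0.01 | 10-per-investigator specialties | 9% | 14% | 19% |
| 0.01 | Pain Units | 8% | 12% | 16% |
| 0.05 | 10-per-investigator specialties | 24% | 38% | 46% |
| 0.05 | Pain Units | 20% | 32% | 41% |
| 0.10 | 10-per-investigator specialties | 36% | 51% | 59% |
| 0.10 | Pain Units | 30% | 46% | 54% |

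A beta-binomial simulation (20,000 runs per cell) agrees to within about one point; its highest value at ICC 0.05 is 47%. A Welch t-test on site percentages from the same simulated data stays at about 5% in every cell. At ICC 0 the patient-level comparison also holds 5%.

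**6. Half-width of one specialty's 95% CI (m = 80, ICC 0.05).** Binomial: 1.96 × √(0.25/n). Clustered: t × √(0.25 × D/n), with t on (departments − 1) df.
- Medical Oncology, n = 12 × 80 = 960: 3.2 points binomial; 2.201 × √(0.25 × 4.95/960) = 7.9 points clustered (11 df).
- Hematology, n = 6 × 80 = 480: 4.5 points binomial; 2.571 × √(0.25 × 4.95/480) = 13 points clustered (5 df).
- Pain Units, n = 24 × 40 = 960: 3.2 points binomial; 2.069 × √(0.25 × 2.95/960) = 5.7 points clustered (23 df).

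At D = 4.95 a nominal 95% binomial interval covers the specialty's underlying prevalence 2Φ(1.96/√4.95) − 1 = 62% of the time.

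**The case against.** **No test is planned.** The analysis is described as exploratory and descriptive, and specialty is one breakdown among several. A reader might infer that the study would declare a specialty difference. The documents contain no test, contrast or decision rule that would do so, and the error rates above belong to a comparison a reader might make. This stands. It does not rescue the intervals, because Protocol 10.1 gives seeing the difference as the purpose, and an interval can be too narrow without a test.

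**The CI method is not stated.** A reader might infer that the SAP prescribes binomial intervals. It does not: a pooled ratio can carry a clustered interval, and the table index in SAP Appendix 1 is redacted. Binomial is an inference from the pooled ratio, the table shell and the ±1% arithmetic.

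**The target may be the participating departments only.** The primary objective refers to participating sites, and Protocol 6.2 lists extrapolation as a limitation. If these departments are the whole population of interest, patient-level error is defensible. But the objective also speaks of a representative cohort, and a difference between specialties is naturally read beyond the sampled departments. The documents leave this open.

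**The ICC may be small.** The Introduction's remark concerns clinical focus, gives no figure, and all sites must apply the Davies algorithm. Some variation between clinics may itself be due to specialty. This is fair, and is why a range is shown. With about two departments per hospital (66/33), a shared hospital effect would also partly cancel between specialties; the department effect would not.

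**No listed objective compares specialties.** A reader might take this contrast as a headline result; the primary and secondary objectives do not name it.

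**Conclusion.** The point holds in a conditional form. The specialty breakdown pools patients over departments, specialty does not vary within a department, and nothing readable brings site in. If the intervals are simple binomial ones, as the evidence indicates, they leave out variation between departments, and chance differences between departments could be read as the specialty difference that Protocol 10.1 wants to see.

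The size rests on the assumed ICC, on one investigator per site, on the department split implied by the quotas, on 36 to 124 pain patients per site (half in Pain Units), and on departments standing for their specialty more widely. On that basis the false-positive rate of a nominal 5% patient-level comparison involving Medical Oncology is about 8 to 19% at ICC 0.01, 20 to 47% at 0.05 and 30 to 60% at 0.10. Hematology is the weakest cell, with about 6 departments. A reader who divides 66 sites evenly over five specialties gets about 13 each, but the quotas do not support that split and it hides this weakness.

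This should be changed, but it does not undermine the primary estimate as such.

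**What to change.** In the specialty item of SAP 5.2, and in Protocol 10.1:
- Name the CI method. Compute each specialty's interval with site as the cluster and a small-sample t reference, or from site-level percentages. With about 6 Hematology departments, the site-level version is the safer choice there.
- Base any statement that specialties differ on a site-level comparison, or on a model with specialty as a fixed effect and site as a random effect. Consider hospital as well if it can be estimated with about two departments each.
- Report, for each specialty, the number of departments and the range of site-level prevalences beside the interval.
- State whether the specialty results describe only the participating departments or the specialties more widely.

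The cost is SAP wording and a few lines of code. Site ID is already a database identifier (Protocol 9.4), so no new data are needed. Protocol section 10 already requires changes to the planned analyses to be described in a revised SAP before data collection is complete. The downside is wider specialty intervals, most of all for Hematology (about 4.5 to 13 points at ICC 0.05 and 80 patients per site), and fewer differences that look clear.
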